## **7 STUDY ASSESSMENTS**

### **7.1 Criteria for Evaluation**

#### **7.1.1     *Efficacy***

##### **7.1.1.1     *7-Point Ordinal Scale of Clinical Status***

The following 7-point ordinal scale of clinical status ([Cao et al 2020](#)) will be used to assess the ordinal scale secondary endpoints. The ordinal scale score is to be documented daily on study through Day 28 for all patients, including those who have been discharged from the hospital.

1. Not hospitalized with resumption of normal activities
2. Not hospitalized but unable to resume normal activities
3. Hospitalization, not requiring supplemental oxygen
4. Hospitalization, requiring supplemental oxygen not meeting criteria for categories 5 or 6
5. Hospitalization, on non-invasive positive pressure ventilation or high-flow nasal cannula

6. Hospitalization, requiring IMV and/or ECMO
7. Death

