**Table 3 Ordinal Scale of Clinical Status (adapted from Cao et al.)**

Ordinal Value and Description
1. Not hospitalized with resumption of normal activities
2. Not hospitalized but unable to resume normal activities
3. Hospitalization, not requiring supplemental oxygen
4. Hospitalization, requiring supplemental oxygen not meeting criteria for categories 5 or 6
5. Hospitalization, on non-invasive positive pressure ventilation or high-flow nasal cannula
6. Hospitalization, requiring IMV and/or ECMO
7. Death

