### **6.1 Primary Efficacy Endpoint**

The primary endpoint is the proportion of patients with progression to IMV and/or ECMO or death by Day 28 (+/- 2 days) for the Intent-to-Treat (ITT) Population. Patients will be considered to have progression to IMV and/or ECMO or death based on the [Cao et al. \(Table 3\)](#) clinical status assessment of 6 or 7. Specifically, the proportion of patients with progression to IMV and/or ECMO or death by Day 28 (+/- 2 days) will be calculated in each treatment arm as:

- (Number of patients with clinical status of 6 or 7 at any time on or before Day 28 (+/- 2 days)) / (Number of patients in the ITT population)

Patients who discontinued early and did not progress to IMV and/or ECMO or death (a clinical status of 6 or 7) will be considered as having progression unless they were discharged from the clinical facility (discharge date is not missing), in which case they will be considered non-progression.

Patients will be summarized based on the randomized (planned) treatment arm. Patients can meet this endpoint in two ways by progressing to IMV and/or ECMO or dying.

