## 6.2 Secondary Efficacy Endpoints

### 6.2.1 Number of Ventilator-Free Days

The number of total ventilator-free days is defined as the number of total days that patients are alive and not intubated, from Day 1 to Day 28. The number of total ventilator-free days will be calculated as:

- Number of ventilator free days = Number of total days with clinical status assessment of 5 or less from Day 1 until Day 28

Ventilator-free days includes all episodes a patient is not on IMV and/or ECMO and report a clinical status form of 5 or less from Day 1 to Day 28.

Patients who discontinued early will be considered as being ventilator-free up to Day 28 if they were discharged from the clinical facility (discharge date is not missing), in which case they will be considered as not having an event of IMV and/or ECMO up to Day 28. Patients who discontinued early and were not discharged from the clinical facility will be considered as being ventilator-free up to the time of study discontinuation.

### 6.2.2 Mortality Rate at Days 15 and 28

The 15-day mortality rate is defined as the proportion of patients with outcome of death during the 15 days following randomization. The Day 15 mortality rate is calculated as:

- $(\text{Number of patients that die by Day 15}) / (\text{Number of patients in the ITT population})$

The 28-day mortality rate is defined as the proportion of patients with outcome of death during the 28 days following randomization. The Day 28 mortality rate is calculated as:

- $(\text{Number of patients that die by Day 28}) / (\text{Number of patients in the ITT population})$

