#### **7.4.1 Primary Efficacy Analysis**

The primary efficacy analysis is the proportion of patients with progression to IMV and/or ECMO or death by Day 28 in the Intent-to-Treat Population.

The primary efficacy endpoint of proportion of patients with progression to IMV and/or ECMO or death will be compared between treatment arms using the Cochran-Mantel-Haenszel (CMH) test stratified by randomization stratification factors age (< 60 years versus  $\geq$  60 years) and 7-point clinical status scale (baseline 3 or 4 versus 5) as entered in the IXRS. The point estimates and 95% confidence intervals of the proportion of patients who progress to IMV and/or ECMO or death will be presented by treatment arm. The CMH odds ratio, difference in progression rates, and associated 95% confidence intervals will be presented.

Patients who discontinued early and did not progress to IMV and/or ECMO or death (a clinical status of 6 or 7) will be considered as having progression unless they were discharged from the clinical facility (discharge date is not missing), in which case they will be considered non-progression.

To evaluate the impact of missing data on the primary analysis, two sensitivity analyses will be performed:

1. A conservative analysis in the ITT population that considers all patients who discontinued early and did not progress to IMV and/or ECMO or death (a clinical status of 6 or 7) as having progression regardless of hospital discharge status.
2. An analysis in the ITT population that considers patients who discontinue early and did not progress to IMV and/or ECMO or death (a clinical status of 6 or 7) as having non-progression.

An additional analysis of the time to event (IMV/ECMO or Death) will be performed.

The time to IMV/ECMO or Death will be calculated as the earliest date of a clinical status assessment of 6 or 7 – date of randomization + 1. Table 6 provides the rules for IMV/ECMO or death events and censoring for the time to event analysis.

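### For early leavers with no recorded status 6 or 7, the primary analysis treats any discharge date as non-progression, whatever the destination or last known status

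*SAP*

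**What the plan says.** SAP 6.1 sets a cautious default and one exception. An early leaver with no status 6 or 7 on record is counted as progression, "unless they were discharged from the clinical facility (discharge date is not missing"; a patient who meets that exception counts as non-progression. SAP 7.4.1 repeats this for the primary analysis without further conditions.

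SAP 6.2.1 uses the same test for ventilator-free days. An early leaver "will be considered as being ventilator-free up to Day 28 if they were discharged from the clinical facility (discharge date is not missing"; an early leaver who was not discharged is credited only up to the time of study discontinuation.

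SAP 7.4.1 adds two sensitivity analyses. The first counts every early leaver without a 6 or 7 "as having progression regardless of hospital discharge status". The second counts all of them as non-progression.

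On follow-up, Protocol 7.1.1.1 requires a daily ordinal score to Day 28, also after a patient has left hospital. Protocol 7.1.4.8 adds weekly contact, with record review for patients who cannot be reached.

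Neither document defines the clinical facility or mentions transfer, hospice or discharge destination. The discharge-day assessments in Protocol 7.1.4.7 include the ordinal score but no destination item.

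**The concern.** The default of progression exists because the outcome of an early leaver is unknown. An exception is reasonable where there is evidence of recovery, and going home is such evidence. A discharge date is weaker: it shows only that the patient left a facility. Two kinds of patient can carry that date without having recovered:

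- a patient moved to another hospital or to hospice, if the site enters the move as a discharge;
- a patient discharged home, readmitted at status 3 to 5, who then withdraws. Protocol 8.1.4.1 anticipates readmission by listing rehospitalization after discharge as a seriousness criterion.

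If such a patient leaves the study before a 6 or 7 is recorded, the primary analysis enters a success for someone whose outcome is unknown and who was not known to have recovered. The ordinal scale already separates the states that matter: categories 1 and 2, such as "Not hospitalized but unable to resume normal activities", are out of hospital, and 3 to 5 are in hospital. The rule does not use it.

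**Working it through.** **1. The plan's own figure.** Inputs from SAP 3.4: 13.5% versus 26.5%, one-sided alpha 0.10, 80% power, about 200 patients at 1:1.

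n per arm = [z(0.90)·√(2p̄q̄) + z(0.80)·√(p1q1 + p2q2)]² / d², with p̄ = 0.20 and d = 0.13

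= [1.2816 × 0.5657 + 0.8416 × 0.5582]² / 0.0169 = 84.5, so 85 per arm.

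With the continuity correction this becomes 100 per arm, 200 in total, which matches the plan. Uncorrected power at 100 per arm is 84.9%. The sample size is not at issue.

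**2. The rule applied case by case.** All rows are early leavers with no recorded 6 or 7. In rows 2 to 4 the discharge date is taken as present.

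| Patient | Primary | Sensitivity 1 | Sensitivity 2 | Ventilator-free credit |
|---|---|---|---|---|
| 1. Discharged home well, then lost | non-progression | progression | non-progression | to Day 28 |
| 2. Transferred, entered as discharge, then withdraws | non-progression | progression | non-progression | to Day 28 |
| 3. Discharged to hospice, then withdraws | non-progression | progression | non-progression | to Day 28 |
| 4. Discharged, readmitted at 3 to 5, then withdraws | non-progression | progression | non-progression | to Day 28 |
| 5. Never discharged, withdraws | progression | progression | non-progression | to discontinuation |

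None of the three analyses separates row 1 from rows 2 to 4.

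**3. Effect of re-scoring.** The documents give no counts, so these are assumed. The test is an unstratified pooled z at n = 100 per arm, standing in for the stratified CMH test:

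z = (difference in proportions) / √(2p̄(1 − p̄)/n)

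The start is the design rates rounded to 27 placebo and 14 pacritinib events: p̄ = 0.205, z = 0.13/0.0571 = 2.28, one-sided p = 0.011.

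| Patients re-scored as progression | Placebo vs pacritinib | One-sided p |
|---|---|---|
| 3, pacritinib only | 27 vs 17 | 0.044 |
| 5, pacritinib only | 27 vs 19 | 0.089 |
| 6, pacritinib only | 27 vs 20 | 0.122 |
| 5 in each arm | 32 vs 19 | 0.017 |
| 9 in each arm | 36 vs 23 | 0.022 |

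Near the threshold one patient is enough: 26 vs 18 gives 0.086 and 26 vs 19 gives 0.118. That start is chosen for closeness to 0.10 and is not a planning value.

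**4. Effect on operating characteristics, under assumptions.** If the rule hid the same share f of true events in both arms, the difference becomes 13.0 × (1 − f) points:

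- f = 5%: 12.4 points, power 83.1%
- f = 10%: 11.7 points, power 81.1%
- f = 20%: 10.4 points, power 76.8%

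If the true rate were 26.5% in both arms and events were hidden in the pacritinib arm only, the one-sided type I error of 0.10 would become about 0.17 with 2 hidden per 100, 0.21 with 3 and 0.32 with 5.

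**5. What the sensitivity analyses cover.** Each arm's rate under a corrected rule must lie between its rates under sensitivity analyses 2 and 1. The comparison between arms need not. Suppose each arm has six early leavers, all with a discharge date; all six on pacritinib belong to rows 2 to 4 and all six on placebo to row 1. Sensitivity 2 gives 27 vs 14 (p = 0.011), sensitivity 1 gives 33 vs 20 (p = 0.019), and correct scoring gives 27 vs 20 (p = 0.122). The split is extreme, but it shows that agreement of the two analyses does not settle the matter.

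**The case against.** The strongest reply has four parts.

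- **The group is small.** A reader might infer that every transferred or hospice patient is scored as a success. The documents do not support that. The rule reaches only patients who discontinue early with no 6 or 7 on record. Patients who stay in the study are scored daily to Day 28 after discharge, records are reviewed for those who cannot be reached, and deaths during the study go on the eCRF (Protocol 8.1.4.4). This stands and limits the point. It does not remove it: under Protocol 4.2 a patient may withdraw consent for all procedures, and data are then used only up to that date.
- **Transfers may not be coded as discharges.** The protocol treats discharge as a move to outpatient status, and a patient in another hospital is still hospitalized on the scale. This too stands: misclassification of transfers is possible, not established. The readmission case does not depend on it, because that patient was truly discharged and, read literally, keeps a discharge date.
- **The sensitivity analyses already test the rule.** They bracket each arm's rate, and the time-to-event analysis censors patients lost to follow-up at their last assessment (SAP Table 6). But they do not correct the primary result, and sensitivity 1 also turns true recoveries into progression.
- **One-sided examples exaggerate.** A reader might infer bias in favour of pacritinib. The trial is double-blind and the documents give no reason for imbalance; with balanced re-scoring little changes. This stands.

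A simple replacement test of last status 1 or 2 would also err. A patient discharged home well could have a discharge-day score of 3 or 4 and be counted as progression, and a status of 2 does not exclude hospice at home.

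**Conclusion.** The point holds in limited form. As written, the primary rule converts an unknown outcome into non-progression on the strength of a date field, for early leavers without a recorded 6 or 7. Followed literally, it gives the wrong answer for a patient readmitted at status 3 to 5 who then withdraws, and for a transfer or hospice move if the site codes it as a discharge. The same test inflates ventilator-free days for these patients.

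The size cannot be found from the documents, which give neither the number of early leavers nor their destinations. Each such patient is worth 1 percentage point in an arm of 100. The effect is small if balanced between arms. It matters if the cases are concentrated in one arm or the result lies close to 0.10. All p-values here rest on assumed counts and an unstratified test. The rule should be tightened, but nothing here shows that the primary result is biased or in which direction.

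**What to change.** Before unblinding, replace the discharge-date test in SAP 6.1, 7.4.1 and 6.2.1 with: discharged to a non-acute, non-hospice setting (confirmed by discharge destination or by a post-discharge status of 1 or 2), and not known to be rehospitalized at the last recorded assessment. A post-discharge score is specified because the discharge-day score may still reflect the hospital stay. Since status 2 is compatible with home hospice, the non-hospice condition applies even where the score is used as confirmation.

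In 6.1 and 7.4.1, all other early leavers without a 6 or 7 keep the SAP's default of progression. In 6.2.1, they are credited as ventilator-free only up to discontinuation. Both sensitivity analyses can stay as written.

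The cost is SAP wording plus a check of discharge destination in the records of the few early leavers, since the protocol's discharge-day list does not include that item.

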## 6.2 Secondary Efficacy Endpoints

### 6.2.1 Number of Ventilator-Free Days

The number of total ventilator-free days is defined as the number of total days that patients are alive and not intubated, from Day 1 to Day 28. The number of total ventilator-free days will be calculated as:

- Number of ventilator free days = Number of total days with clinical status assessment of 5 or less from Day 1 until Day 28

Ventilator-free days includes all episodes a patient is not on IMV and/or ECMO and report a clinical status form of 5 or less from Day 1 to Day 28.

Patients who discontinued early will be considered as being ventilator-free up to Day 28 if they were discharged from the clinical facility (discharge date is not missing), in which case they will be considered as not having an event of IMV and/or ECMO up to Day 28. Patients who discontinued early and were not discharged from the clinical facility will be considered as being ventilator-free up to the time of study discontinuation.

### 6.2.2 Mortality Rate at Days 15 and 28

The 15-day mortality rate is defined as the proportion of patients with outcome of death during the 15 days following randomization. The Day 15 mortality rate is calculated as:

- $(\text{Number of patients that die by Day 15}) / (\text{Number of patients in the ITT population})$

The 28-day mortality rate is defined as the proportion of patients with outcome of death during the 28 days following randomization. The Day 28 mortality rate is calculated as:

- $(\text{Number of patients that die by Day 28}) / (\text{Number of patients in the ITT population})$

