### **2.3.2 *Secondary Objectives***

1. To compare the number of ventilator-free days, defined as the number of days that patients are alive and not intubated, from randomization to Day 28 between pacritinib + SOC versus placebo + SOC
2. To compare the mortality rate between pacritinib + SOC versus placebo + SOC at Day 28
3. To compare the mortality rate between pacritinib + SOC versus placebo + SOC at Day 15
4. To compare the time to improvement by at least 2 points relative to Baseline on the 7-point ordinal scale of clinical status between pacritinib + SOC versus placebo + SOC
5. To compare the clinical status assessed by the 7-point ordinal scale of clinical status at Days 8, 15, 22, and 28 between pacritinib + SOC versus placebo + SOC
6. To compare the rate of use of immunomodulatory agents as treatment for COVID-19 during the 28 days following randomization between pacritinib + SOC versus placebo + SOC
7. To evaluate the toxicity profile of pacritinib therapy in hospitalized patients with severe COVID-19 with or without cancer

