### **Secondary Endpoints**

The number of ventilator-free days will be presented by treatment arm using descriptive statistics including mean, median, standard deviation, interquartile range, and may include frequency distributions.

The mortality rate at Day 28 will be compared between treatment arms using the CMH test stratified by age (< 60 years versus  $\geq$  60 years) and baseline 7-point clinical status scale (baseline 3 or 4 versus 5). The point estimates and 95% confidence intervals of the mortality rates at

Day 28 will be presented by treatment arm. The CMH odds ratio, difference in mortality rates at Day 28, and associated 95% confidence intervals will be presented.

The mortality rate at Day 15 will be compared between treatment arms using the CMH test stratified by age (< 60 years versus  $\geq$  60 years) and baseline 7-point clinical status scale (baseline 3 or 4 versus 5). The point estimates and 95% confidence intervals of the mortality rates at Day 15 will be presented by treatment arm. The CMH odds ratio, difference in mortality rates at Day 15, and associated 95% confidence intervals will be presented.

The time from randomization to improvement by at least 2 points relative to Baseline on the 7-point clinical status will be compared between treatment arms using a stratified log-rank test stratified by age (< 60 years versus  $\geq$  60 years) and baseline 7-point clinical status scale (baseline 3 or 4 versus 5). All enrolled patients will have a score between 3 and 5 by virtue of being hospitalized and non-intubated; therefore, patients who progress from 3 to 1, from 4 to 2, or from 5 to 3 will have met the definition of improvement. Kaplan-Meier methods will be used to estimate time to improvement by treatment arm. Summary statistics, including median time to improvement and corresponding 95% confidence intervals, will be presented by treatment arm. The hazard ratio (HR) for time to improvement by treatment arm will be estimated using a stratified Cox proportional hazards model stratified by age (< 60 years versus  $\geq$  60 years) and baseline 7-point clinical status scale (baseline 3 or 4 versus 5).

The clinical status assessed by the 7-point ordinal scale of clinical status at Days 8, 15, 22, and 28 will be presented by treatment arm using counts and percent of patients at each level of the 7-point scale score.

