#### **7.4.2 Secondary Efficacy Analysis**

##### **7.4.2.1 Number of Ventilator-Free Days**

The number of ventilator-free days will be presented by treatment arm using descriptive statistics. The 95% confidence intervals will be provided. The treatment arm comparison will be performed using the Wilcoxon rank sum test.

In addition, the number of patients that remain ventilator-free for certain clinically significant thresholds (e.g. 21 days) may be summarized.

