##### **7.4.2.2 Mortality Rate at Day 15 and 28**

The Day 15 and Day 28 mortality rates and associated 95% confidence interval will be summarized by treatment arm.

The mortality rate at Day 15 and Day 28 will be compared between treatment arms using the CMH test stratified by age (< 60 years versus  $\geq$  60 years) and baseline 7-point clinical status scale (baseline 3 or 4 versus 5). The point estimates and 95% confidence intervals of the mortality rates at Day 15 and Day 28 will be presented by treatment arm. The CMH odds ratio, difference in mortality rates at Day 15 and Day 28, and associated 95% confidence intervals will be presented.

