## **9 CHANGES FROM PROTOCOL-SPECIFIED ANALYSIS**

No changes from the protocol-specified analysis are planned.

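### The rank test on ventilator-free days can place a death above a ventilated survivor, because the count gives death no worst value

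*SAP*

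**What the plan says.** SAP 6.2.1 gives the formula: "Number of ventilator free days = Number of total days with clinical status assessment of 5 or less from Day 1 until Day 28". In SAP Table 3, status 6 is invasive ventilation or ECMO and status 7 is death, so neither kind of day is counted. The only special rules in 6.2.1 concern early discontinuation: "Patients who discontinued early will be considered as being ventilator-free up to Day 28 if they were discharged from the clinical facility", while those not discharged are credited up to the time they left the study. No rule gives death a value of its own.

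SAP 7.4.2.1 adds: "The treatment arm comparison will be performed using the Wilcoxon rank sum test". SAP 7.1 limits comparative testing to places where it is stated, so this is a deliberate comparison.

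Protocol 11.1.1 defines the endpoint in the same way as the SAP. The objective in Protocol 2.3.2 reads "To compare the number of ventilator-free days, defined as the number of days that patients are alive and not intubated". For the analysis, Protocol 11.3 says "The number of ventilator-free days will be presented by treatment arm using descriptive statistics including mean, median, standard deviation, interquartile range" and names no test, and SAP 9 states "No changes from the protocol-specified analysis are planned".

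Deaths are counted elsewhere. They are events in the primary composite (SAP 6.1), and under SAP 7.4.2.2 the Day 15 and Day 28 mortality rates "will be compared between treatment arms using the CMH test stratified by age" and baseline clinical status.

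**The concern.** As a total to be described, days alive and off the ventilator is coherent. A rank test makes a further demand: it uses only the order of the scores and treats a higher score as a better outcome. Here a late death without ventilation outranks a patient who needed a week or two of ventilation and survived. If one arm has more deaths and fewer ventilated survivors than the other, the two differences can offset each other in the ranks. The p-value for this endpoint could then look neutral when mortality is not.

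**Working it through.** The documents give no sizing or expected value for ventilator-free days, so there is no plan figure to reproduce. The only design input used is about 200 patients randomized 1:1, that is 100 per arm (SAP 3.4). All outcome rates and timings below are assumptions.

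**1. When a death outranks a survivor.** Take the day of death as status 7.
- Death on Day d, never ventilated: score d-1.
- Survivor ventilated v days: score 28-v.
- The death ranks higher when d-1 > 28-v, that is v ≥ 30-d.
- Example: d = 22 gives 21; v = 8 gives 20.

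**2. How often, among pairs.** Full enumeration with survivors ventilated 7 to 21 days (15 values):

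| Day of death | Pairs | Death ranks better | Tied |
|---|---|---|---|
| 5-28 | 24 × 15 = 360 | 195 (54%) | 15 (4%) |
| 2-14 | 13 × 15 = 195 | 21 (11%) | 7 (4%) |
| 15-28 | 14 × 15 = 210 | 174 (83%) | 8 (4%) |

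These pairs cover never-ventilated deaths only. The result depends heavily on how late deaths occur.

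**3. Trial level, no death after ventilation.** Assume the composite is 20% in both arms. Arm A has 15% deaths and 5% ventilated survivors; arm B has 7% and 13%. The other 80% score 28. Death days are uniform on 5-28 and ventilated days uniform on 7-21.

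Mean days as written:
- Arm A: 0.15 × 15.5 + 0.05 × 14 + 0.80 × 28 = 25.4
- Arm B: 0.07 × 15.5 + 0.13 × 14 + 0.80 × 28 = 25.3

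The Wilcoxon test compares P(A > B) plus half the ties with 0.5. From step 2, a death beats a ventilated survivor with probability (195 + 7.5)/360 = 0.5625.
- Terms common to both codings: 0.80 × 0.80/2 + 0.80 × 0.20 + 0.05 × 0.13/2 + 0.15 × 0.07/2 = 0.4885
- As written, add 0.15 × 0.13 × 0.5625 + 0.05 × 0.07 × 0.4375 = 0.0125, giving 0.501
- Deaths ranked last, add 0.05 × 0.07 = 0.0035, giving 0.492

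The tie-corrected standard error is about √[201/(12 × 100 × 100) × (1 - 0.8³)] = 0.0286. So z is about +0.001/0.0286 = +0.03 as written and -0.008/0.0286 = -0.28 with deaths last.

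**4. Varying the share of deaths that follow ventilation.** Simulation, 20,000 trials per row (standard error of mean z about 0.007). A death after ventilation loses a further 1 to d-1 days, uniformly. Negative z means harm in arm A. Harm is flagged at one-sided 0.10, borrowed from the primary endpoint for scale only.

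| Deaths after ventilation | Mean z, as written | Mean z, deaths last | Harm flagged, as written | Harm flagged, deaths last |
|---|---|---|---|---|
| 0% | +0.04 | -0.27 | 9% | 16% |
| 50% | -0.07 | -0.27 | 11% | 16% |
| 80% | -0.14 | -0.28 | 13% | 16% |
| 100% | -0.18 | -0.28 | 14% | 16% |

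The first row agrees with step 3. In the same trials, a simple two-proportion comparison of mortality flags harm in 71%.

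**The case against.** The strongest reply is that nothing in the plan is contradicted. The protocol chose days alive and off the ventilator, the SAP computes exactly that, and death does count because every day from death onward adds zero. Ranking all deaths last turns the tested variable into a different, composite score, and no rule in the documents requires it. That stands: this is an analysis choice that can be improved, and the SAP does not depart from the endpoint definition.

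The scenario is also built to show the problem, with equal composite rates so that extra deaths are exactly offset by fewer ventilated survivors. When most deaths follow ventilation, little is lost, and even the corrected ranking detects the excess deaths weakly. Both points are fair and keep the concern small. They do not make the order a sensible one for a rank test.

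Two stronger readings are tempting but not supported.

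- A reader might infer from the discharge rule in SAP 6.2.1 that a death after discharge scores 28, the best value. The rule covers only patients who left the study early, its stated consequence concerns ventilation and ECMO events, and the definition in the same section still requires the patient to be alive. Protocol 7.1.1.1 and 7.1.4.8 continue daily scores to Day 28 after discharge, so a death in a patient still on study is recorded as status 7. Only someone discharged, then discontinued early, then known to have died by Day 28 is left unclear. That group is narrow, and the documents give no basis for sizing it.
- A reader might infer from SAP 9 that the Wilcoxon test is an undeclared departure from the protocol. The objective is worded as a comparison, and Protocol 11 leaves analysis details to the SAP. Naming a test can be read as such detail, so an entry in SAP 9 is record-keeping.

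**Conclusion.** The concern holds as a minor point about one secondary endpoint. That the test can rank a death above a ventilated survivor follows from the SAP formula alone. How much this matters depends on inputs the documents do not give: the number and timing of deaths, how many follow ventilation, and how long survivors are ventilated. Under the assumptions shown, the count as written removes essentially all of a z of about -0.3 if no death follows ventilation, and about a third of it if all do. In these scenarios the test is blunted; they do not show it favouring the arm with more deaths to any material degree. The primary composite and the mortality comparisons are untouched, so the trial's main conclusions do not depend on this.

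**What to change.** - In SAP 7.4.2.1, for the between-arm test only, rank every death by Day 28 below all survivors, for example with a value of -1. A value of 0 would tie with a survivor ventilated on all 28 days.
- Keep the present count as the descriptive summary.
- Add one sentence to SAP 6.2.1 saying that credit stops at death, including for a patient who was discharged, discontinued early and is known to have died by Day 28.
- Optionally, note the test and the ranking of deaths in SAP 9.

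Alternatively, drop the test and stay descriptive, as in Protocol 11.3.

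The cost is two or three sentences and minor programming. There are two downsides: the tested score would differ from the summarized one, so the two could point in different directions, and early and late deaths would rank alike in the test.
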